### ***Sub aim analysis***

We will estimate the difference in endothelial function from baseline to 2 hours after surgery and baseline to 24 hours after surgery using separate paired t-tests on the subset of 40 patients with these measurements. We will also summarize RHI over time graphically.

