## SPECIFIC AIMS

Systemic inflammation caused by exposure to cardiopulmonary bypass or other conditions such as sepsis, ischemia-reperfusion, trauma, major surgery and prolonged hyperglycemia leads to endothelial activation by circulating cytokines and subsequent injury to glycocalyx and endothelium.[\[1, 2\]](#) Intravascular solutions used for plasma volume replacement, such as human albumin 5%, demonstrate endothelial protective effects which may mitigate the postoperative inflammatory response and consequent endothelial injury.[\[3, 4\]](#) Administration of hydroxyethyl starch (HES) solutions, which have known adverse effects on endothelial function, increases mortality and kidney injury in patients with sepsis [\[5, 6\]](#) perhaps due to aggravation of endothelial and glycocalyceal injury.[\[7-9\]](#) Whether endothelial function is improved in cardiac surgical patients receiving plasma volume resuscitation with 5% human albumin compared with HES solutions, however, is unknown. Our proposed investigation will *test the primary hypothesis* that **postoperative endothelial function**, measured with peripheral arterial tonometry as reactive hyperemia index (RHI) within 2 hours following surgery, **is improved in cardiac surgical patients who are randomized to receive human albumin for plasma volume replacement**, compared with 6% HES solutions. Secondarily, we *hypothesize* that **patients who receive 5% human albumin will have reduced plasma concentrations of molecular biomarkers of glycocalyceal injury (syndecan 1 and endocan)** compared with those who receive 6% HES solutions. *If plasma volume resuscitation with 5% human albumin preserves perioperative endothelial function, kidney dysfunction and other organ injury following cardiac surgery may be reduced.*

**Specific aim 1. To determine whether human albumin 5% improves postoperative endothelial function compared with 6% HES (130/0.4).** Endothelial function will be assessed 2 hours following surgery by measuring RHI using peripheral arterial tonometry (EndoPAT, Itamar Medical Inc., Caesarea, Israel), a well validated tool used in endothelial dysfunction diagnostics and cardiovascular risk stratification.[\[10-12\]](#) We *hypothesize* that patients who receive human albumin 5% for intravascular volume replacement during surgery will have improved endothelial function at 2 hours following surgery compared with those who receive 6% HES (130/0.4).

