**Sub-aim 1.** Our preliminary data suggest that post-operative endothelial function is poorly correlated with baseline (preoperative) endothelial function. In a subset of patients, we will describe the expected changes that occur in endothelial function during the perioperative period (baseline, early postoperative, 24 hours postoperative). We will assess this for 40 patients (20 per group), at baseline, within 2 hours after surgery, and 24 hours after surgery. We *hypothesize* that there will be a decline in endothelial function from baseline to 2 hours after surgery and no significant difference in function between baseline and at 24 hours after surgery.

**Specific aim 2. To determine whether human albumin 5% reduces plasma biomarkers of endothelial and glycocalyceal damage.** We will measure plasma concentrations of syndecan 1 and endocan at baseline (before surgery), and 1 and 24 hours following surgery. Syndecan 1 and endocan are components of glycocalyx, and increased blood concentrations of these molecules indicate glycocalyceal shedding and endothelial dysfunction.[\[13, 14\]](#) We *hypothesize* that patients who receive human albumin 5% for intravascular volume replacement during surgery will have reduced concentrations of syndecan 1 and endocan at 1 and 24 hours following surgery compared with those who receive 6% HES (130/0.4).

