### **Sample size analysis**

This will be limited to the 85 patients expected to enroll in the SHARP study. Moerland et al found the a mean  $\pm$  SD of  $1.8 \pm 0.5$  in a healthy study population and  $2.9 \pm 1.4$  in a population with renal injury [M. Moerland, A. J. Kales, L. Schrier, M. G. J. van Dongen, D. Bradnock, and J. Burggraaf, "Evaluation of the EndoPAT as a Tool to Assess Endothelial Function," International Journal of Vascular Medicine, vol. 2012, Article ID 904141, 8 pages, 2012. doi:10.1155/2012/904141]. We expect similar variability in our cardiac surgery population. Assuming a conservative standard deviation of 1.4, we will have 90% power at the 0.05 significance level to detect an difference of 1.0 or greater in our study population. We will have 65% power to detect a clinically important difference of 0.73 (i.e., 25% of 2.9).

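### The sub-aim tests perioperative change in RHI with the two arms pooled; adding treatment arm would show each arm's 2-hour change and slightly tighten the error term, at no cost in data

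*Combined protocol and SAP*

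**What the plan says.** Sub-aim 1 (Specific Aims) sets the purpose: "we will describe the expected changes that occur in endothelial function during the perioperative period". The sample is split by randomised group: "We will assess this for 40 patients (20 per group), at baseline, within 2 hours after surgery, and 24 hours after surgery". The hypothesis, a decline at 2 hours and no significant difference from baseline at 24 hours, is stated for patients overall and not by arm.

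The Sub aim analysis section compares baseline with each later time "using separate paired t-tests on the subset of 40 patients with these measurements". It adds a graph of RHI over time and does not say whether the graph is by arm.

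Specific aim 1 expects the arms to differ at the first postoperative time: "patients who receive human albumin 5% for intravascular volume replacement during surgery will have improved endothelial function at 2 hours", compared with HES. The Sample size analysis section puts figures on this. It claims "90% power at the 0.05 significance level to detect an difference of 1.0 or greater in our study population", and it calls a difference of 0.73 clinically important, with 65% power.

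The Secondary analyses section allots 0.0125 to each sub-aim or secondary analysis. Its biomarker models do contain group and a group-by-time test.

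**The concern.** Randomised arms share the same expected baseline, so a difference in RHI at 2 hours is also a difference in the change from baseline to 2 hours. A paired t-test on all 40 patients then estimates the average of two different changes and leaves the gap between them in the error term.

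Nothing else in the plan fills the gap. The primary analysis models postoperative RHI, not change. The adjustment described under Statistical analysis covers imbalanced baseline and procedural characteristics, not treatment. The biomarker models follow both group and time, but no RHI analysis does.

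What is at stake is mainly interpretation. The sub-aim exists to describe how endothelial function moves around surgery, and a reader would take its one number as applying to patients in either arm. A small loss of precision at 2 hours comes second.

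**Working it through.** **Inputs from the plan.** Subset of 40, 20 per arm (Sub-aim 1). Arm difference D in RHI at 2 hours of 0.73 or 1.0, SD of RHI 1.4, total 85 patients (Sample size analysis). Sub-aim alpha 0.0125 (Secondary analyses).

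**Assumptions.** Allocation 42/43 for the 85; two-sided tests; the same SD at both times; baseline-to-postoperative correlation rho of 0 to 0.2. Sub-aim 1 calls the correlation poor but gives no figure.

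**1. The plan's own power.** Two-sample t-test, 83 df, standard error 1.4 × sqrt(1/42 + 1/43). A difference of 1.0 gives 90.2% (stated 90%). A difference of 0.73 gives 66.1%, or 65.5% with the unrounded 0.725 (stated 65%). The plan's figures reproduce. It gives no power or precision for the sub-aim.

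**2. Distance of each arm from the pooled mean.** With 20 per arm this is D/2: 0.73/2 = 0.37 and 1.0/2 = 0.50 RHI units. It does not depend on the SD or the correlation.

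**3. Error SD of the 2-hour change.** Within arm, s_w = 1.4 × sqrt(2(1 − rho)). Pooled, the expected variance is s_w² + (40/39) × D²/4. For example, at rho 0 and D = 1.0: sqrt(3.920 + 0.256) = 2.044, against 1.980.

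**4. Power for an arm-averaged change.** Noncentral t at two-sided 0.0125: 39 df pooled, 38 df with arm in the model. The changes of 0.5 and 1.0 are illustrative, because the documents give no expected size.

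| rho | D | s_w | pooled SD | inflation | power, change 0.5 (pooled v arm) | power, change 1.0 (pooled v arm) |
|---|---|---|---|---|---|---|
| 0 | 0.73 | 1.980 | 2.014 | 1.7% | 16.1% v 16.7% | 69.7% v 71.4% |
| 0 | 1.0 | 1.980 | 2.044 | 3.2% | 15.6% v 16.7% | 68.2% v 71.4% |
| 0.2 | 0.73 | 1.771 | 1.809 | 2.2% | 20.6% v 21.6% | 80.4% v 82.3% |
| 0.2 | 1.0 | 1.771 | 1.842 | 4.0% | 19.8% v 21.6% | 78.8% v 82.3% |

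The gain is about 1 to 4 points. The change detectable with 80% power falls from 1.11–1.12 to 1.09 at rho 0, and from 1.00–1.01 to 0.98 at rho 0.2.

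**5. Validity of the pooled test.** In a simulation of 40,000 trials with D = 1.0 and no average change, the pooled test rejected in 0.010 (rho 0) and 0.009 (rho 0.2), against a nominal 0.0125. It errs on the conservative side.

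**6. Sensitivity.** At SD 1.4 the inflation is 3.4 to 6.3% at rho 0.5 and 8.4 to 15.2% at rho 0.8. At SD 0.5, which the Sample size analysis section also cites, it is 13 to 28% for rho 0 to 0.2.

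**7. Precision by arm.** The 95% half-width with 20 per arm, using the pooled within-arm SD (38 df, t = 2.024), is 2.024 × 1.771/sqrt(20) = 0.80 at rho 0.2 and 2.024 × 1.980/sqrt(20) = 0.90 at rho 0.

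**The case against.** The best defence is that the method fits the stated aim. The sub-aim is descriptive, its hypothesis is not by arm, and the between-arm question on RHI belongs to the primary analysis in the whole cohort. With 20 complete patients per arm, the pooled mean equals the arm-averaged change that a model with arm would give. This stands, and it means the planned test need not be abandoned.

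It is also true that by-arm estimates would be imprecise. Half-widths of 0.80 to 0.90 exceed the 0.37 to 0.50 that separates each arm from the average, so by-arm results would seldom prove that the average misdescribes an arm. That is a reason to report them as estimates with intervals rather than to test them. It is not a reason to omit them.

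Three stronger readings are tempting, and the documents do not support them.

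- **A pooled decline could be a decline under HES alone.** With pooled decline M, the albumin arm declines by M − D/2, so it shows no decline only if M is at most D/2, that is 0.37 to 0.50. The plan gives no expected decline. The Preliminary data section reports worsening in three patients but no size for it on the RHI scale.
- **The power loss is large.** Taking the SD of change as 1.0, with D = 1.0 and a decline of 0.5, gives 59% pooled against 70% with arm. But with an RHI SD of 1.4, that SD of change implies rho = 1 − 1.0²/(2 × 1.4²) = 0.74, which is hard to square with the poor correlation reported in Sub-aim 1.
- **Both tests suffer.** An RHI difference between arms is hypothesised at 2 hours only.

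**Conclusion.** The point holds as one of interpretation at 2 hours, with a small gain in precision. If the primary hypothesis is true with a difference of 0.73 to 1.0, the sub-aim will report a 2-hour change that is 0.37 to 0.50 RHI units away from the true change in each arm, and the plan has no analysis that shows this. The error SD at 2 hours is about 2 to 4% larger than it need be, given SD 1.4 and rho 0 to 0.2. The loss would be greater if RHI proved less variable or more strongly correlated than the plan suggests. The pooled test itself is sound for the arm-averaged change, so no false-positive problem arises, and nothing is claimed about the 24-hour comparison. This is an inexpensive improvement, not a flaw that threatens the sub-aim.

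**What to change.** Include arm in the sub-aim analysis. Either of two forms will do: a regression of each change on centred arm (coded −0.5 and +0.5, so that the intercept is the equally weighted average change), or a mixed model on the three RHI times with arm, time and arm-by-time.

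- Keep the arm-averaged change as the test, at 0.0125.
- Report each arm's change with a 95% confidence interval, labelled descriptive and not tested. The SAP should state the expected half-width of about 0.8 to 0.9.
- State that the graph of RHI over time will be drawn by arm.

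The cost is a few lines of SAP text and slightly more programming. It needs no further patients, measurements or alpha.

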### **Secondary analyses**

The albumin effect on each biomarker (i.e., syndecan 1 and endocan) at 1 hour and 24 hours after surgery will be assessed using separate repeated measures linear regression models adjusting for within-subject correlation, baseline biomarkers and imbalanced baseline variables. We will assess the heterogeneity of the treatment effect over time by testing the group-by-time interaction for each model using a criterion of  $P < 0.15$ . If heterogeneity is detected, we will analyze outcomes separately at each time, using additional Bonferroni correction as necessary. We expect that biomarkers will be lognormally distributed, so we will perform a log transformation and compare groups on ratio of geometric means. An alpha of 0.05 will be used for each set of the primary and sub/secondary analyses, with a significance criterion of 0.05 for the primary analysis and 0.0125 for each sub or secondary analysis (i.e., 0.05/4, Bonferroni). We will complete analyses using SAS version 9.4 or newer (SAS Institute, Cary, NC, USA) and R version 3.2.3 or newer (R Project for Statistical Computing, Vienna, Austria).

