### **Experimental Protocol**

Cardiac surgical patients enrolled in the SHARP study will be randomized to either 5% human albumin or 6% HES on entrance to the operating room. Anesthetic and Surgical management will follow protocol established by SHARP study including administration of a blinded study solution which contains 5% human albumin or 6% HES following separation from cardiopulmonary bypass. Blood will be collected for measurement of baseline syndecan 1 and endocan following arterial line and urinary catheter placement. At 1 and 24 hours following surgery completion, blood will be collected for measurement of syndecan 1 and endocan. Within two hours of ICU arrival, PAT will be performed in ICU. In a subset of patients, PAT will be performed preoperatively and at 24 hours after surgery.

Because vasoactive substances may influence EndoPAT measurement, we will collect data on use of all preoperative antihypertensive medications that have direct or indirect effect on smooth muscle relaxation. Cardiac surgery patients often need intraoperative and postoperative inotropic support. Data on use of perioperative vasoactive medications that may influence EndoPAT results including epinephrine, norepinephrine, vasopressin, milrinone, nitroglycerine, nitroprusside, and sedatives such as propofol, dexmedetomidine and others will be recorded and subsequently adjusted for in the analysis. Data on transfusion of packed red blood cells and blood components will be collected from Anesthesia Record Keeping System. Minimum hematocrit (HCT) will be approximately 23% following cardiopulmonary bypass and 21% on cardiopulmonary bypass. Packed blood cell, platelets, fresh frozen plasma and/or cryoprecipitate transfusions may be administered as determined necessary by attending anesthesiologist or surgeon. Any imbalance in blood product transfusion between the two study groups will be adjusted for in analysis.

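### With one baseline slope for both times, baseline adjustment drops out of the biomarker group-by-time test; a baseline-by-time term would restore it

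*Combined protocol and SAP*

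**What the plan says.** Specific aim 2 is stated at two times: it expects "reduced concentrations of syndecan 1 and endocan at 1 and 24 hours following surgery" in the albumin arm. Under Experimental Protocol the sampling matches this: "At 1 and 24 hours following surgery completion, blood will be collected for measurement of syndecan 1 and endocan", after a baseline sample.

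Under Secondary analyses each biomarker gets its own model, described as "separate repeated measures linear regression models adjusting for within-subject correlation, baseline biomarkers and imbalanced baseline variables". On scale, "we will perform a log transformation and compare groups on ratio of geometric means". Then: "We will assess the heterogeneity of the treatment effect over time by testing the group-by-time interaction for each model", at P < 0.15. The consequence is also stated: "If heterogeneity is detected, we will analyze outcomes separately at each time, using additional Bonferroni correction as necessary". If heterogeneity is not detected, one albumin effect across both times is implied. The significance criterion is "0.0125 for each sub or secondary analysis (i.e., 0.05/4, Bonferroni").

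Group-by-time is the only interaction named. The section does not say whether the baseline slope may differ between 1 h and 24 h. It names no within-patient covariance structure and does not restate the covariates for the separate-time analyses.

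**The concern.** A programmer following this section would most likely enter the baseline biomarker as an ordinary covariate with one slope for both times. A term that contributes equally at 1 h and 24 h vanishes when one is subtracted from the other, and the group-by-time test is a test of that subtraction. The models are described as baseline-adjusted, yet the adjustment would not reach the test that settles how each biomarker is reported.

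Two things are at stake. First, the test is noisier than it needs to be if baseline predicts the two times unequally. That is plausible here: release soon after bypass could swamp baseline at 1 h, with values moving back towards baseline by 24 h. A chance baseline difference between arms would then also move the contrast. Second, the screening test and the follow-up do not match. Separate analyses that keep the baseline covariate each fit their own slope, so the difference between the two effects then reported is not the quantity that was tested.

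**Working it through.** **Stated figures.** The secondary criterion reproduces (0.05/4 = 0.0125) and is not affected. The documents give no variance or correlation for either biomarker, so there is no stated precision figure to reproduce.

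**Inputs.** From the documents: 85 patients (Sample size analysis), log scale, two post-baseline times, P < 0.15. Assumed: arms of 42 and 43; SD 1 on the log scale at baseline and at both later times; baseline correlation r1 = 0.2 to 0.4 with the 1 h value and r24 = 0.6 to 0.7 with the 24 h value; 1 h to 24 h correlation ρ = 0.4 to 0.6; complete pairs.

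**Step 1: the cancellation.** With one slope b, the model means at the two times both contain b × baseline. Their difference D = Y24 − Y1 contains (b − b) × baseline = 0. In one simulated data set of 85 patients:

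| Quantity | Estimate |
|---|---|
| Raw between-arm differences, 1 h and 24 h | 0.1875 and 0.1578 |
| Raw difference in change (24 h minus 1 h) | −0.0297 |
| Group-by-time, one slope, compound symmetry | −0.0297 |
| Group-by-time, one slope, unstructured | −0.0297 |
| Separate baseline-adjusted effects, 1 h and 24 h | 0.1603 and 0.0967 |
| Their difference | −0.0636 |
| Group-by-time with baseline-by-time added | −0.0636 |

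The one-slope test examines the raw change. The model with baseline-by-time examines the same difference that the separate analyses would report.

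**Step 2: variance of the contrast.** Per patient it is 2(1 − ρ) with one slope and 2(1 − ρ) − (r24 − r1)² with time-specific slopes. The gap r24 − r1 runs from 0.6 − 0.4 = 0.2 to 0.7 − 0.2 = 0.5.

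- Smallest excess (gap 0.2, ρ = 0.4): 1.20/1.16 = 1.03, or 3%.
- Middle (0.3, 0.7, ρ = 0.5): 1.00/0.84 = 1.19, or 19%.
- Largest excess (gap 0.5, ρ = 0.6): 0.80/0.55 = 1.45, or 45%.
- Equal slopes (gap 0): 0%.

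**Step 3: power of the P < 0.15 test.** Take a true difference in effects of 0.5 SD. The standard error is √(1/42 + 1/43) = 0.217 times the square root of the Step 2 variance. Power is Φ(0.5/SE − 1.44), plus a negligible opposite tail.

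| ρ | One slope | Time-specific slopes, gap 0.2 | Time-specific slopes, gap 0.5 |
|---|---|---|---|
| 0.5 | SE 0.217, 81% | SE 0.213, 82% | SE 0.188, 89% |
| 0.6 | SE 0.194, 87% | SE 0.189, 89% | SE 0.161, 95% |

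**Step 4: chance imbalance.** The baseline difference between arms has SE 0.217 SD, so 0.25/0.217 = 1.15 and an imbalance of at least 0.25 SD has about a 25% chance. At 0.25 SD the unadjusted contrast shifts by 0.25 × (r24 − r1), which is 0.05 to 0.125 SD.

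**Step 5: what is not affected.** In simulations without a treatment effect (1,500 replicates per scenario), mean estimates stayed near zero and the one-slope test rejected in 14% to 15% of runs. Under compound symmetry the pooled effect equals an analysis of covariance of the two-time mean (0.1285 both ways in the Step 1 data set). Under an unstructured covariance its sampling SD was 0.1704 against 0.1701 with baseline-by-time (r1 0.3, r24 0.6, ρ 0.6), and 0.1660 against 0.1619 in an extreme case (0.2, 0.7, 0.5).

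**The case against.** The plan never says that one slope is used; it is silent. That stands: this is the plain reading of an under-specified model, not a stated choice. But silence leaves the default, and the default has the weakness shown.

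A reader might infer that the albumin effects at 1 h and 24 h are themselves under-adjusted. The documents do not support this. When heterogeneity is detected, each time is analysed on its own, with its own baseline slope if baseline is kept. When it is not, the pooled effect is reported, and that is adjusted exactly or nearly so. Only time-specific effects read from the one-slope joint model would be mis-adjusted (too little at the time with the steeper slope, too much at the other), and the plan does not call for those.

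It can also be said that nothing invalid happens: the test holds its level, and a wrong screening result only switches the form of reporting. That is correct and limits the point to efficiency and coherence. Finally, the size rests on assumed correlations, all with baseline predicting 24 h better than 1 h. This too stands: at the mild end power rises by 1 to 2 points, and with equal slopes not at all.

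The rule of adjusting for variables with a standardised difference above 0.25 does not help, because any baseline variable entered with one slope cancels in the same way.

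**Conclusion.** The point holds for the group-by-time test alone. On the plain reading and with complete pairs, that test carries no baseline adjustment and does not match the separate-time effects reported after it. If some pairs are incomplete, the cancellation is no longer exact.

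Under the assumed correlations and arms of 42 and 43, the contrast variance is 3% to 45% larger than it needs to be. The power forgone for a 0.5 SD difference is about 1 to 8 percentage points at both of the between-time correlations tabulated. These figures depend on unequal baseline slopes, which the documents neither support nor exclude.

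It would go too far to infer bias or an inflated error rate: a chance imbalance can move the contrast in a given trial, but over randomisation the 15% level is kept. The primary analysis, the sample size and the allocation of alpha are untouched. This is a minor point, worth making because the remedy is cheap.

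**What to change.** In Secondary analyses, specify for each biomarker: log(biomarker) on group, time, group-by-time, centred log(baseline biomarker), and centred log(baseline biomarker)-by-time, with an unstructured within-patient covariance. Take the group-by-time test from this model. State that log(baseline biomarker) stays as a covariate in the separate-time analyses. With complete pairs, the tested contrast then equals the difference between the two reported effects.

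The cost is one model term and a sentence or two of text, with no new data or patients. The downside is one degree of freedom per biomarker, about 1% of variance with 85 patients, which is wasted only if the two slopes turn out equal.

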### **Human albumin 5% has beneficial effects on endothelial and glycocalyceal function compared with HES solutions**

Human albumin has demonstrated beneficial effects on vascular endothelial and glycocalyceal function in ex vivo models. It prevents fluid extravasation more effectively compared with crystalloid or synthetic HES solutions in an ex vivo heart model, and has been shown to inhibit binding of activated polymorphonuclear leukocytes to bovine aortic endothelial cells. [\[3\]](#) [\[4\]](#) Shear stress-mediated nitric oxide release and coronary vasodilatation is potentiated with administration of human albumin compared with HES solutions.[\[9\]](#) Further, binding of neutrophil-derived myeloperoxidase to bovine aortic endothelial cells, a mediator of multiple oxidative and nitric oxide-consuming reactions, is inhibited by human serum albumin, while it is amplified by HES solutions.[\[4\]](#) Thus the protective characteristics of plasma volume administration with human albumin may reduce endothelial injury in the kidney and other organs, and, ultimately, reduce postoperative organ dysfunction in cardiac surgical patients, especially compared with use of HES solutions.

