### Randomization

Patients will be randomized to receive either HES 130/0.4 (Voluven) or albumin 5% for treatment of intraoperative acute hypovolemia. (Treatment assignments will be generated using a reproducible algorithm in the PLAN procedure in SAS statistical software. Randomization will be conducted using an existing password-protected web randomization site used for all clinical trials coordinated by the Department of Outcomes Research and maintained by the Anesthesia Institute statistical team.)

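### The biomarker analysis makes no allowance for postoperative dilution, although the randomised fluids act on plasma volume, so a lower concentration cannot by itself be read as less glycocalyx shedding

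*Combined protocol and SAP*

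**What the plan says.** Specific aim 2 defines the measurement: "We will measure plasma concentrations of syndecan 1 and endocan at baseline (before surgery), and 1 and 24 hours following surgery". It also gives the interpretation: "increased blood concentrations of these molecules indicate glycocalyceal shedding and endothelial dysfunction". The hypothesis is lower concentrations with albumin.

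The Secondary analyses section sets the scale, "we will perform a log transformation and compare groups on ratio of geometric means", and the covariates, "adjusting for within-subject correlation, baseline biomarkers and imbalanced baseline variables". Each secondary test is judged at 0.0125.

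On the fluids, the Specific Aims introduce them this way: "Intravascular solutions used for plasma volume replacement, such as human albumin 5%, demonstrate endothelial protective effects". The background section comparing albumin with HES says of albumin: "It prevents fluid extravasation more effectively compared with crystalloid or synthetic HES solutions in an ex vivo heart model". It gives no magnitude.

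On indication and timing, the Randomization section says "Patients will be randomized to receive either HES 130/0.4 (Voluven) or albumin 5% for treatment of intraoperative acute hypovolemia". The Experimental Protocol describes "administration of a blinded study solution which contains 5% human albumin or 6% HES following separation from cardiopulmonary bypass" and places the baseline sample after arterial line and urinary catheter placement.

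Haematocrit appears only as an approximate minimum in the transfusion text of the Experimental Protocol. No section indexes the biomarkers to haematocrit, haemoglobin, total protein or plasma volume, or names study-fluid volume as a covariate.

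**The concern.** A plasma concentration depends on the amount of marker in the circulation and on the plasma volume it is dissolved in. Here the randomised treatment can act on that volume. If one arm carries more plasma volume at the postoperative draw, its concentrations are lower even when shedding is identical.

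The two biomarkers would move together, so agreement between syndecan 1 and endocan would not expose the problem. If the albumin arm were the more diluted, a volume effect could be reported as protection of the glycocalyx. If the HES arm were the more diluted, a true benefit of albumin could be masked. Because aim 2 reads concentration directly as shedding, the plan as written has no means of telling these cases apart.

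**Working it through.** **The plan's own figures.** The secondary criterion reproduces: 0.05/4 = 0.0125. The Sample size analysis section gives power only for RHI (SD 1.4, 85 patients). With 42 vs 43 patients (1:1 allocation assumed), a two-sided noncentral t calculation gives 90.2% for a difference of 1.0 (stated 90%) and 66.1% for 0.73 (stated 65%). These concern the primary outcome only. The plan states no SD, effect size or power for the biomarkers.

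**Do the planned steps remove dilution?**
- *Log transformation.* If plasma volume in one arm is larger by a fraction x, its concentrations are divided by (1 + x). On the log scale that is a shift of −ln(1 + x), which goes unchanged into the ratio of geometric means.
- *Baseline biomarker.* The study fluid follows the baseline draw, so baseline cannot carry later dilution.
- *Imbalance rule (ASD > 0.25).* The Statistical analysis section applies it to baseline and procedural characteristics. Study-fluid volume could be counted as procedural but is not named, and infused volume is not retained volume.
- *Blood-product adjustment.* The Experimental Protocol promises this for imbalance between arms. It addresses transfusion, not dilution by study fluid.

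**Size under assumed values.** Assumptions: x = 5–20% (for example 0.15 L on 3.0 L up to 0.5 L on 2.5 L); SD of log concentration 0.3, 0.5 or 0.7 after baseline adjustment; equal shedding. None of these is in the documents. Ratio (more diluted arm over the other) = 1/(1 + x). The rejection rate uses a two-sided z-test at 0.0125 with SE = SD × √(1/42 + 1/43) = SD × 0.217.

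| x | Ratio | Rejection, SD 0.3 | SD 0.5 | SD 0.7 |
|---|---|---|---|---|
| 5% | 0.952 | 4.1% | 2.2% | 1.7% |
| 10% | 0.909 | 15.1% | 5.3% | 3.2% |
| 15% | 0.870 | 36.3% | 11.3% | 5.8% |
| 20% | 0.833 | 61.9% | 20.7% | 9.7% |

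The nominal rate is 1.25%.

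**Ratio needed for significance.** exp(−2.498 × SE) gives:
- SD 0.3: exp(−2.498 × 0.0651) = 0.85
- SD 0.5: exp(−2.498 × 0.1085) = 0.76
- SD 0.7: exp(−2.498 × 0.1519) = 0.68

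At SD 0.5 or 0.7, no ratio in the table reaches significance through dilution alone. At SD 0.3, only the 20% case does.

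**Averaging over time.** The model estimates one effect over 1 and 24 hours unless the interaction has P < 0.15. If dilution differed only at 1 hour (assumption) and the two times had equal weight, the ratio would be the square root of the table value: 0.98 at x = 5%, 0.95 at 10%, 0.91 at 20%.

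**Can a correction work?** In simulation (x = 5%, 10%, 20%; 4,000 runs per cell), correcting by a same-sample dilution marker with log error SD 0.04 returned the ratio to about 1.00 and rejection to 1.0–1.6%. That marker was idealised. The haematocrit correction multiplies C_t by [(1 − Hct_t)/(1 − Hct_0)] × (Hct_0/Hct_t), which assumes constant red-cell mass. To see how it can fail, assume baseline haematocrit 40%, then 25% in the HES arm and 27% in the albumin arm, with the difference between arms due only to bleeding:
- HES: (0.75/0.60) × (0.40/0.25) = 2.00
- Albumin: (0.73/0.60) × (0.40/0.27) = 1.80

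The correction alone then produces a ratio of 1.80/2.00 = 0.90 in favour of albumin, about the size of the artefact from 10% dilution.

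**The case against.** The strongest reply has four parts.

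1. *Direction.* A reader might infer that the bias runs in albumin's favour. The documents do not establish this. The support is one ex vivo statement without a magnitude, and the fluid is given for hypovolaemia, so a less retained fluid may be given in larger volume and the arms may end equally diluted. This stands.
2. *Consequence.* A reader might infer that dilution would by itself yield a significant aim 2 result. At the middle and upper assumed SDs the ratios fall short of what significance requires, and 61.9% needs the smallest SD together with the largest dilution. The simple volume ratio also ignores continuing release, clearance and redistribution. This stands. What remains is that dilution adds to or subtracts from any true effect and raises the rejection rate above nominal.
3. *Validity.* Plasma concentration is the declared outcome, so comparing concentrations is legitimate. This stands: the problem is the step from concentration to shedding.
4. *Remedy.* Haematocrit correction is distorted by bleeding and transfusion. The plan expects transfusion, and the parent trial compares the same fluids on coagulation, so blood loss may differ by arm. The untransfused subset is selected after randomisation. This stands too, and means the corrected analysis cannot decide the conclusion.

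The parent SHARP protocol is not supplied and may already collect haematocrit or fluid volumes. That would lower the cost of the change, but this plan does not use such data for the biomarkers.

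**Conclusion.** The point holds as a limit on interpretation. Syndecan 1 and endocan are compared without any account of postoperative dilution, the randomised fluids act on plasma volume, and none of the planned adjustments removes a difference arising after the baseline draw. Whether the arms will differ in dilution, which way and by how much cannot be learned from the documents. The 0.95–0.83 range rests on assumed volumes, and every rejection rate rests also on an assumed SD. The documents do not support calling the aim 2 comparison invalid or predicting a false finding for albumin. They do support saying that a lower concentration could not be separated from a volume effect with the data and analyses now specified. Only the secondary biomarker analyses are concerned; RHI is not a plasma concentration.

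**What to change.** Keep the planned log-scale model as the main analysis, and add the following.

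- **Data.** Record the haematocrit nearest each biomarker draw, study-fluid volume, blood loss and red-cell transfusion, or take them from SHARP if already collected. Report all of them by arm.
- **Analysis.** In the Secondary analyses section, pre-specify a supportive analysis of haematocrit-corrected concentrations, using the formula above in the same model, in all patients. Label any analysis of untransfused patients exploratory.
- **Stated limit.** Say that the correction assumes stable red-cell mass and can be biased if bleeding or transfusion differs by arm.
- **Wording.** Do not make agreement between corrected and uncorrected ratios a pass/fail condition. Report a positive aim 2 result as a lower plasma concentration. Attribute it to reduced glycocalyx shedding only with the corrected estimate and the arm differences in dilution, blood loss and transfusion shown alongside.

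The cost is one or two recorded values per draw and one extra model per biomarker. The downside is that the correction is itself imperfect. Treatment, sample size and the primary analysis do not change.
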